# 2 STUDY OBJECTIVES AND ENDPOINTS

Table 2-1         Study objectives and endpoints		
Objectives	Endpoints	
Efficacy		
Primary		
• To compare the clinical efficacy of an experimental 0.454% w/w SnF 2 dentifrice for the relief of DH, as elicited by an evaporative air stimulus (with Schiff sensitivity score), against a negative control dentifrice, when used twice daily for 8 weeks.	Change from Baseline in Schiff sensitivity score at 8 weeks.	
Secondary		
• To compare the clinical efficacy of an experimental $0.454\%$ w/w SnF 2 dentifrice for the relief of DH, as elicited by a tactile stimulus (yeaple probe), against a negative control dentifrice, when used twice daily for 8 weeks.	
 
Change from Baseline in tactile threshold at 8 weeks.
 
	
Exploratory		
• To compare the clinical efficacy of an experimental 0.454% w/w SnF2 dentifrice for the relief of DH, as elicited by an evaporative air stimulus (with Schiff sensitivity score), against a positive control dentifrice, when used twice daily for 4 and 8 weeks.	• Change from Baseline in Schiff sensitivity score at 4 and 8 weeks.	
• To compare the clinical efficacy of an experimental 0.454% w/w SnF 2 dentifrice for the relief of DH, as elicited by an evaporative air stimulus (with Schiff sensitivity score), against a negative control dentifrice, when used twice daily for 4 weeks.	• Change from Baseline in Schiff sensitivity score at 4 weeks.	
• To compare the clinical efficacy of an experimental $0.454\%$ w/w SnF 2 dentifrice for the relief of DH, as elicited by a tactile stimulus (yeaple probe), against a negative control dentifrice,	Change from Baseline in tactile threshold at 4 weeks.	
GlaxoSmithKline Consumer	Healthcare Confidential	

Template Version Effective: 22-Jun-2017

Page 13 of 60

Final 1.0 Clinical Protocol

Final 1.0 Chinical Protocol		
when used twice daily for 4 weeks.		
• To compare the clinical efficacy of an experimental 0.454% w/w SnF dentifrice for the relief of DH, as elicited by a tactile stimulus (yeaple probe) against a positive control dentifriced when used twice daily for 4 and 8 weeks	threshold at 4 and 8 weeks.	
• To compare the clinical efficacy of positive control dentifrice for the relief of DH, as elicited by a tactile stimulu (yeaple probe), against a negative control dentifrice, when used twice daily for and 8 weeks.	f threshold at 4 and 8 weeks. s 1	
• To compare the clinical efficacy of positive control dentifrice for the relief o DH, as elicited by an evaporative ai stimulus (with Schiff sensitivity score against a negative control dentifrice when used twice daily for 4 and 8 weeks	f sensitivity score at 4 and 8 weeks r )	
Safety		
• To evaluate the safety and ora tolerability of the test dentifrices when used twice daily for 8 weeks.		

This study will be considered successful if there is a statistically significant difference in the primary efficacy variable, change from baseline in Schiff sensitivity score, after 8 weeks of treatment. The difference should be viewed as clinically relevant in addition to being statistically significant

# 3 STUDY DESIGN AND SUBJECT POPULATION

This will be a single centre, randomized, controlled, examiner-blind, 3 treatment arm, parallel group design study, stratified by maximum baseline Schiff sensitivity score (of the two selected test teeth), with a treatment period of 8 weeks, to investigate the clinical effectiveness of an experimental  $SnF_2$  dentifice in the reduction of DH. DH will be assessed at Baseline, and after 4 and 8 weeks treatment.

The study will be conducted in healthy subjects with pre-existing self-reported and clinically diagnosed tooth sensitivity at Screening, in a Chinese population. A sufficient number of subjects will be screened to randomize approximately 180 subjects to ensure 165 subjects complete the study.

GlaxoSmithKline Consumer Healthcare Confidential Template Version Effective: 22-Jun-2017 Page 14 of 60

	Document Name	208153 Clinical Protocol.docx		
	Туре	Version	Document Identifier	Effective Date
	eldo clinical doc	3.0; Most-Recent; Effective; CURRENT	090032d580d852b1	3-Aua-2017 05:58:20
	Reason For Issue	Auto Issue		0
St	tannous fluoride			

The age range over which an individual can experience DH is wide (from early teens to 70s) [Fischer, 1992], with peak incidence known to occur between the ages of 20-40 years [Graf, 1977; Flynn, 1985]. The fall in prevalence observed in later decades reflects age related changes in the dentine and pulp of the tooth which act to reduce dentine permeability and the tooth's response to the external triggers of DH [Seltzer, 1975; Pashley, 2008]. Given that the dental pain experienced by older members of the population is less likely to be diagnosed as DH [Rees, 2000], the age range of 18-70 selected for this study targets individuals suffering from tooth sensitivity which is most likely due to DH. This will facilitate recruitment and minimise inconvenience to older participants who may be more likely to be rejected at Screening.

An acclimatization period of 2-6 weeks will be included in this study, given that 2 weeks is understood to be an expected amount of time to minimize the potential for carry over effects from prior use of anti-sensitivity products.

In line with Chinese Ministry of Health guidelines [Ministry of Health (China), 2010] for the testing of functional dentifrices (desensitizing), a standard fluoride dentifrice with no specific anti-sensitivity, anti-gingivitis and anti-plaque activity (Chinese marketed Colgate Triple Protection) will be included as the negative control. A Chinese marketed positive control dentifrice with sensitivity benefits (Crest 7-Effects Strengthen Dental Enamel toothpaste, containing stannous chloride (SnCl2)) will also be included in this study design as a benchmark of performance in the Chinese population.

# 4 SUBJECT SELECTION

This study can fulfill its objectives only if appropriate subjects are enrolled. The following eligibility criteria are designed to select subjects for whom participation in the study is considered appropriate. All relevant medical and nonmedical conditions should be taken into consideration when deciding whether a particular subject is suitable for this protocol.

# 4.1 Inclusion Criteria

Subject eligibility should be reviewed and documented by an appropriate member of the investigator's study team before subjects are included in the study.

Subjects must meet all of the following inclusion criteria to be eligible for enrollment into the study:

- 1. Evidence of a personally signed and dated informed consent indicating the subject has been informed of all pertinent aspects of the study before any assessment is performed.
- 2. Male and female subjects who, at the time of screening, are between the ages of 18 and 70 years, inclusive.
- 3. Subjects who are willing and able to comply with scheduled visits, treatment plan, and other study procedures.

GlaxoSmithKline Consumer Healthcare Confidential Template Version Effective: 22-Jun-2017 Page 15 of 60

Final 1.0 Clinical Protocol

- 4. Good general and mental health, in the opinion of the investigator or medically qualified designee.
- 5. Male subjects able to father children and female subjects of childbearing potential and at risk for pregnancy must agree to use a highly effective method of contraception throughout the study and for at least 5 days after the last dose of assigned treatment, refer to Section 4.4.2 for guidance. Female subjects who are not of childbearing potential must meet requirements in Section 4.4.2.
- 6. The following oral and dental inclusions will apply at **Screening (Visit 1)**:
  - a) Self-reported history of dentinal hypersensitivity lasting more than six months but not more than 10 years.
  - b) Good general oral health, with a minimum of 20 natural teeth.
  - c) Minimum of 2 accessible non-adjacent teeth (incisors, canines, pre-molars), preferably in different quadrants, that meet all of the following criteria:
    - i. Signs of facial/cervical gingival recession and/or signs of erosion or abrasion (EAR).
    - ii. Tooth with Modified Gingival Index (MGI) score =0 adjacent to the test area (exposed dentine) only [Lobene, 1986] and a clinical mobility of ≤1.
    - iii. Tooth with signs of sensitivity measured by a qualifying tactile stimulus (Yeaple  $\leq 20g$ ) qualifying evaporative air assessment (Schiff sensitivity score  $\geq 2$ ).

The following dental inclusions will apply at **Baseline (Visit 2)**:

d) Minimum of two, non-adjacent accessible teeth (incisors, canines, pre-molars), with signs of sensitivity, measured by response to a qualifying tactile stimulus (Yeaple ≤20g) and evaporative air assessment (Schiff sensitivity score ≥2). The two selected test teeth must have also qualified at Screening for this criteria.

**Note:** The Investigator will select two *Test Teeth* from those which meet *both* the tactile threshold and Schiff sensitivity score criteria, in addition to meeting all other criteria. *Test Teeth* should not be adjacent to each other and preferably in different quadrants.

## 4.2 Exclusion Criteria

Subjects with any of the following characteristics/conditions will not be included in the study:

- 1. Subjects who are investigational site staff members directly involved in the conduct of the study and their family members, site staff members otherwise supervised by the investigator, or subjects who are GSK employees directly involved in the conduct of the study.
- 2. Participation in another clinical study (including cosmetic studies), or receipt of an investigational drug within 30 days prior to the Screening visit and/or during study participation.

GlaxoSmithKline Consumer Healthcare Confidential Template Version Effective: 22-Jun-2017

Page 16 of 60

Final 1.0 Clinical Protocol

- 3. Participation in another tooth desensitizing treatment study within 8 weeks of the Screening visit.
- 4. Acute or chronic medical or psychiatric condition that may increase the risk associated with study participation or investigational product administration or may interfere with the interpretation of study results and, in the judgment of the investigator, would make the subject inappropriate for entry into this study.
- 5. Pregnant female subjects. This will be confirmed verbally at Screening and confirmed by Urine pregnancy testing (carried out on all female subjects of child bearing potential) at the Baseline visit.
- 6. Breastfeeding female subjects.
- 7. Known or suspected intolerance or hypersensitivity to the study materials (or closely related compounds) or any of their stated ingredients.
- 8. Recent history (within the last year) of alcohol or other substance abuse.
- 9. Unwilling or unable to comply with the lifestyle guidelines described in this protocol.
- 10. Subjects who have previously been enrolled in this study.
- 11. General oral and dental exclusions:
  - a) Dental prophylaxis within 4 weeks of Screening.
  - b) Tongue or lip piercing or presence of dental implants.
  - c) Gross periodontal disease, treatment of periodontal disease (including surgery) within 12 months of Screening, scaling or root planning within 3 months of Screening.
  - d) Teeth bleaching within 8 weeks of Screening.
  - e) Use of an over-the-counter (OTC) desensitizing product (eg. dentifrice) and/or professional desensitizing treatment within 8 weeks of Screening. Subjects will be required to bring their current oral care products to the site in order to verify the absence of known anti-sensitivity ingredients.
- 12. Specific dental exclusions for test teeth:
  - a) Sensitive tooth not expected to respond to treatment with an over-the-counter dentifrice in the opinion of the investigator.
  - b) Tooth with exposed dentine but with deep, defective or facial restorations, teeth used as abutments for fixed or removable partial dentures, teeth with full crowns or veneers, orthodontic bands or cracked enamel. Sensitive teeth with contributing aetiologies other than erosion, abrasion or recession of exposed dentine.
  - c) Tooth with evidence of current or recent caries, or reported treatment of decay within 12 months of Screening.
- 13. Concomitant Medication:
  - a) Daily doses of medication/treatments or traditional herbal ingredients/treatments which, in the opinion of the investigator, could interfere

GlaxoSmithKline Consumer Healthcare Confidential Template Version Effective: 22-Jun-2017 Page 17 of 60

Stannous fluoride

Protocol Number 208153 Final 1.0 Clinical Protocol

with the perception of pain. Examples of such medications include analgesics, anticonvulsants, antihistamines that cause marked or moderate sedation, sedatives, tranquilisers, anti-depressants, mood-altering and anti-inflammatory drugs. Examples of herbal ingredients/treatments include clove oil, olive oil, or other treatments that are directly applied to the oral cavity for the treatment of oral health conditions.

- b) Currently taking antibiotics or has taken antibiotics within 2 weeks of Screening and/or Baseline.
- c) Daily dose of a medication which, in the opinion of the investigator, is causing xerostomia.
- d) Individuals who require antibiotic prophylaxis for dental procedures.
- 14. Any subject who, in the judgment of the investigator, should not participate in the study.

# 4.3 Randomization Criteria

Subjects will be randomized into the study provided they have satisfied all subject selection criteria.

# 4.4 Lifestyle Guidelines

For the duration of the study (Screening to LSLV):

- Eligible subjects will be asked to stop using their regular oral care products from Screening for the duration of the study.
- Use of dental floss will be for the removal of impacted food only.
- Subjects will not be permitted to use any other oral care products (i.e., oral rinses, tongue cleaners, whitening/bleaching products, inter-dental brushes) other than those provided to them in this study.
- Subjects will not be permitted to use any other dental products (other than those provided to them in this study), including home remedies, intended for treating sensitive teeth.
- Subjects will not be permitted to chew gum.

Prior to study days (Baseline to Week 8):

• Subjects will be asked to refrain from all oral hygiene procedures for **at least 8 hours** in order to standardize oral hygiene practices.

## 4.4.1 Dietary and Alcohol Restrictions

Prior to study days (Baseline to Week 8):

GlaxoSmithKline Consumer Healthcare Confidential Template Version Effective: 22-Jun-2017 Page **18** of **60** 

- Subjects will be asked to refrain from eating and drinking for **at least 4 hours**. Before each visit small sips of water will be allowed for the purpose of taking medication, but subjects will be asked to refrain from doing this 1 hour before attending the study site.
- Subjects will be requested to refrain from excessive alcohol consumption for 24 hours prior to the Baseline, Week 4 and Week 8 visits. If in the opinion of the Investigator the subject has consumed an excessive amount of alcohol prior to the visit, every effort will be made to reappoint them to the next day. If this is not possible then the subject should be treated as per Section 6.4.

## 4.4.2 Contraception

All male subjects and female subjects who are of childbearing potential and are sexually active and at risk for pregnancy must agree to use a highly effective method of contraception consistently and correctly for the duration of the active study period and for at least 5 days after the last dose of investigational product. The investigator or his or her designee, in consultation with the subject, will confirm that the subject will select an appropriate method of contraception for the individual subject from the permitted list of contraception methods (see below) and instruct the subject in its consistent and correct use. Subjects need to affirm that they meet the criteria for the correct use of at least 1 of the selected methods of contraception. The investigator or his or her designee will discuss with the subject the need to use highly effective contraception consistently and correctly according to the schedule of activities and document such conversation in the subject's chart. In addition, the investigator or his or her designee will instruct the subject to call immediately if the selected contraception method is discontinued or if pregnancy is known or suspected in the subject or the subject's partner.

Highly effective methods of contraception are those that, alone or in combination, result in a failure rate of less than 1% per year when used consistently and correctly (i.e., perfect use) and include the following:

- 1. Established use of oral, inserted, injected, transdermal, or implanted hormonal methods of contraception is allowed provided the subject plans to remain on the same treatment throughout the entire study and has been using that hormonal contraceptive for an adequate period of time to ensure effectiveness as deemed appropriate by the investigator.
- 2. Correctly placed copper-containing intrauterine device (IUD).
- 3. Male condom or female condom used WITH a spermicide (i.e., foam, gel, film, cream, or suppository). For countries where spermicide is not available or condom plus spermicide is not accepted as highly effective contraception, this option is not appropriate.
- 4. Male sterilization with absence of sperm in the post-vasectomy ejaculate.
- 5. Bilateral tubal ligation / bilateral salpingectomy or bilateral tubal occlusive procedure (provided that occlusion has been confirmed in accordance with the device's label).
- 6. Female who meets the criteria for non-childbearing potential as described below.

GlaxoSmithKline Consumer Healthcare Confidential Template Version Effective: 22-Jun-2017 Page **19** of **60** 

Final 1.0 Clinical Protocol

Female subjects of non-childbearing potential must meet at least one of the following criteria:

- a. Achieved postmenopausal status, defined as follows: cessation of regular menses for at least 12 consecutive months with no alternative pathological or physiological cause; and have a serum follicle-stimulating hormone (FSH) level confirming the post-menopausal state;
- b. Have undergone a documented hysterectomy and/or bilateral oophorectomy;
- c. Have medically confirmed ovarian failure.

All other female subjects (including females with tubal ligations) will be considered to be of childbearing potential.

## 4.5 Screen Failures

Screen failures are defined as subjects who consent to participate in the clinical study but are not subsequently randomized. In order to ensure transparent reporting of screen failure subjects, a minimal set of screen failure information will include demography, screen failure details (e.g., withdrawal of consent), eligibility criteria, and any serious adverse events (SAEs).

Individuals who do not meet the criteria for participation in this study (screen failure) may not be re-screened.

## 4.6 Sponsor's Qualified Medical Personnel

The contact information for the sponsor's appropriately qualified medical/dental personnel for the study is documented in the study contact list located in the study file.

The contact number can be used by investigational staff if they are seeking advice on medical/dental questions or problems; however, it should be used only in the event that the established communication pathways between the investigational site and the study team are not available. It is therefore intended to augment, but not replace, the established communication pathways between the investigational site and the study team for advice on medical/dental questions or problems that may arise during the study. The contact number is not intended for use by the subject directly, and if a subject calls that number, he or she will be directed back to the investigational site.

To facilitate access to appropriately qualified medical/dental personnel on study-related medical/dental questions or problems, subjects are provided with a contact card. The contact card contains, at a minimum, protocol identifiers, subject study numbers, contact information for the investigational site, and contact details in the event that the investigational site staff cannot be reached to provide advice on a medical question or problem identified from the subject's healthcare professional other than the investigator.

GlaxoSmithKline Consumer Healthcare Confidential Template Version Effective: 22-Jun-2017 Page 20 of 60

Final 1.0 Clinical Protocol

# 5 STUDY TREATMENTS

# 5.1 Blinding and Allocation to Treatment/Randomization

This study is described as examiner blind, however, to minimize the potential of unblinding the study statistician, other employees of the sponsor, and vendors acting on behalf of the sponsor, who may influence study outcomes are blinded to the product allocation of subjects. The examiner will be blinded to the treatment received. To ensure the examiner remains blinded throughout the study, the examiner is not permitted in the room whilst product is dispensed, and subjects will be asked not to remove study products from their bags outside of the dispensing room and until they are home. In addition, subjects should be treated in a separate area. The dispensing staff will not be involved in any efficacy assessments during the study.

InVentiv Health will create the randomization schedules and provide to Global Clinical Supplies (GCS). GCS will print the randomization schedules and supply the clinical study site with two versions of the randomization schedule, each in a sealed envelope and clearly marked as either "For Dispensing" or "Emergency Use Only".

The "For Dispensing" schedule will contain the list of randomization numbers only and will not include any coded description, just a letter A, B or C.

The 'Emergency Use Only' randomization schedule will only be removed from the sealed envelope in an emergency situation. This schedule will have a randomization number followed by the letter A, B or C. The schedule will have a footnote with a key for A, B and C identifying the three treatments arms. However, to maintain the blinding of the study as far as possible, all treatment allocations for all randomization numbers on this randomization schedule will be masked with scratch-off panels.

Subjects will be stratified according to their maximum baseline Schiff sensitivity score of the two selected teeth (sensitivity score of 2 or 3) with randomization numbers within each stratum assigned in ascending numerical order as each subject is determined to be fully eligible. The stratification factor will give rise to two strata.

- **Stratum 1:** Maximum Schiff=2. These are subjects with maximum baseline Schiff sensitivity score of 2 for the two selected test teeth.
- **Stratum 2:** Maximum Schiff=3. These are subjects with the maximum baseline Schiff sensitivity score of 3 for the two selected test teeth.

In accordance with the randomization numbers, the subject will receive the study treatment assigned to the corresponding randomization number.

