## 5.2 Breaking the Blind

At the initiation of the study, the study site will be instructed on the method for breaking the blind. The method will be a manual process, whereby only scratch-off panels will be removed

GlaxoSmithKline Consumer Healthcare Confidential Template Version Effective: 22-Jun-2017 Page **21** of **60** 

for subjects that require unblinding. Blinding codes should be broken only in emergency situations for reasons of subject safety. Whenever possible, the investigator or sub-investigator should consult with a member of the study team prior to breaking the blind unless the delay would endanger the subject's health. When the blinding code is broken, the reason must be fully documented and entered in the CRF.

Any AE or SAE associated with breaking the blind must be recorded and reported as specified in this protocol. The study site is required to inform the EC if the blind is broken.

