#### 5.4.2 Preparation and Dispensing

The examiner will be blinded to the treatment received. To ensure the examiner remains blinded throughout the study, the examiner will not be permitted in the room where the test products are stored or dispensed. The product dispensing area will be separate from the subjects' examination area. All study dentifrices will be dispensed by qualified site personnel who are not involved in any study efficacy assessments. The investigational products will be dispensed in blinded fashion to the subject. A second member of site personnel will verify that the correct dentifrice has been dispensed to each subject. A record of the product dispensed to each subject will be recorded in a treatment dispensing log, and assigned against each subject number.

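### Does the shared A/B/C key on the emergency schedule let one code break unblind more than the intended subject?

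*Protocol*

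**What the plan says.** Protocol Section 5.1 has Global Clinical Supplies "supply the clinical study site with two versions of the randomization schedule, each in a sealed envelope", one marked for dispensing and the other for emergency use only. The dispensing schedule lists randomization numbers and "will not include any coded description, just a letter A, B or C". Of the emergency schedule the section says: "This schedule will have a randomization number followed by the letter A, B or C". It then adds: "The schedule will have a footnote with a key for A, B and C identifying the three treatments arms". The next sentence says that, to keep the blind as far as possible, "all treatment allocations for all randomization numbers on this randomization schedule will be masked with scratch-off panels". The section does not say whether the footnote key is also covered.

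Section 5.2 describes a manual break in which panels are removed only "for subjects that require unblinding. Blinding codes should be broken only in emergency situations for reasons of subject safety".

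Several rules keep this material away from the people who score efficacy. Section 5.1 states: "The examiner will be blinded to the treatment received". Section 5.4.2 adds that "the examiner will not be permitted in the room where the test products are stored or dispensed", and that the staff who dispense take no part in efficacy assessments. Section 5.1 allows the emergency schedule out of its envelope only in an emergency. Section 6.4 lists unblinding among the events that require stopping study treatment and/or withdrawal.

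**The concern.** Section 5.2 intends a break to expose only the subject who needs it. The scratch-off panels appear to secure that, but what they hide is a letter, and a letter for the same randomization number is open on the dispensing schedule. What gives the letter meaning is a single key shared by all subjects. Whoever interprets one scratched letter must read at least that line of the key. If that person also has the dispensing letters, the line identifies everyone with the same letter, and the full key identifies everyone.

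The stake would be the blind on scoring. The Schiff score, which carries the primary endpoint, is an examiner's rating from 0 to 3, and Section 7.2.2 has one examiner rate every subject at each visit. Section 1.2.2 describes the trial as examiner-blind only. If that examiner learned a block of allocations, every later Schiff score for those subjects could be affected.

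**Working it through.** **Inputs.** Protocol Section 3 gives three arms. Section 10.1 gives about 180 randomized and 165 completing, about 55 per arm. The allocation ratio is not stated. The completer figure is consistent with equal allocation (165 / 3 = 55), so I assume 180 / 3 = 60 randomized per arm. I also assume that a letter means the same on both lists. The protocol does not say so, but it calls them two versions of one schedule and describes no re-lettering.

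**How many allocations can be decoded after one break?** These are upper bounds.

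| What the person has | Decodable | Share of 180 | Unintended |
|---|---|---|---|
| Emergency sheet only, one panel removed | 1 | 1 / 180 = 0.6% | 0 |
| One subject's product plus the dispensing letters | 60 | 60 / 180 = 33% | 60 − 1 = 59 |
| Readable key plus the dispensing letters | 180 | 100% | 180 − 1 = 179 |

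If arm sizes ran from 55 to 65, the second row would run from 55 / 180 = 31% to 65 / 180 = 36%. The third row also needs the key to be uncovered, on which the protocol is silent. All counts include subjects who have already finished, whose scores can no longer be affected.

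**What would have to happen for a score to be affected?**

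1. A code is broken. Section 5.2 limits this to emergencies, and the documents give no expected frequency.
2. One person has both the opened emergency sheet and the dispensing letters. Those who dispense are the natural holders of the letters, and Sections 5.1 and 5.4.2 keep them out of efficacy assessment.
3. The decoded allocations reach an examiner who still has visits to score. Section 5.1 requires the examiner to be blinded, Section 5.4.2 bars the examiner from the storage and dispensing room, and no section gives an examiner the dispensing letters.

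The plan as written blocks step 3. Dispensing staff who work out what a letter means do not by that alone breach the examiner blind.

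**What would the obvious change achieve?** Suppose the emergency sheet showed the product under each panel and carried no letter and no key.

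| What the person has | Now | After the change |
|---|---|---|
| Emergency sheet only | 1 | 1 |
| One product plus the dispensing letters | 60 | 60 |
| Readable key plus the dispensing letters | 180 | 60 |

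The middle row does not move, because one known product still matches one letter on the dispensing list. If the key is already masked letter by letter, the third row does not arise today and the change achieves nothing. To do better, the dispensing side itself must change. With k letters per product and no key, the bound is 180 / (3k): 60 for k = 1, 30 for k = 2 and 15 for k = 4. Subject-specific kit numbers bring it to 1.

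**The case for a change.** The best case for a change is that the safeguards are incomplete and the remedy is cheap. The rules bar the examiner from a room, but no sentence expressly bars the examiner from the dispensing list or the dispensing log. Section 5.2 names the investigator or sub-investigator in connection with breaking the blind, and Section 7.2.1 speaks of the investigator re-probing a tooth, so the wording does not cleanly separate the code-breaker from the examiner. The documentation and withdrawal rules deal with the subject whose code was broken; they would not reveal that others had been decoded in passing. A sheet without a shared key would rely less on keeping two papers apart.

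Part of this stands. The lists can be joined, and a layout with subject-specific codes would be tighter. It does not show a fault in the trial. The requirement that the examiner be blinded is general and already covers any list or log that would reveal treatment, so a sentence naming those documents would restate it. An investigator who broke a code would still need the dispensing letters to learn about anyone else. Section 5.2 also says the site will be instructed at initiation on how to break the blind; custody of the opened sheet could be covered there, though the documents do not show that it is.

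**Conclusion.** No change to the plan follows. After one break, a person holding both lists could decode up to about 60 of 180 allocations, or up to 180 if the footnote key is uncovered. Both figures rest on equal allocation and common lettering. For anyone without the dispensing letters the figure is 1. These are counts of allocations, not bias, and the documents offer no basis for turning them into an effect on the treatment comparison.

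Followed as written, the protocol keeps the decoded information from the people who score, so no efficacy result is affected. Reformatting the emergency sheet alone would leave the one-arm exposure at about 60. Removing it would take subject-specific dispensing codes, with extra labelling and log work, for no demonstrated gain in any result. A sponsor designing a new code sheet might reasonably prefer that layout; this trial's conclusions do not depend on it.
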